5.5 Pharmacokinetic, Pharmacodynamic, Pharmacogenomic, and Other Biomarker Analyses

5.5.1 Pharmacokinetic Analyses

The PK analysis will be performed on the PK Analysis Set using plasma concentrations of E7386 in combination with pembrolizumab.

Phase 1b

Plasma concentrations of E7386 will be tabulated and summarized by part, dose level, day and time. Plasma concentrations will be summarized using descriptive statistics (number of subjects [n], mean, SD, minimum, median, maximum).

Mean (\pm SD) and individual plasma concentration vs. time profile plots will be produced for each E7386 dose on both linear and semi-log scales for **CCI** **██████████**. The \pm SD bars will only be displayed on the linear-linear scale. Spaghetti plots of individual plasma concentration vs. time profile plots will be produced for each dose level, day and time using linear scales.

PK parameters will be derived by noncompartmental analysis according to User Manual 302-104.00-MNL for the Phase 1b part. PK parameters derived from plasma E7386 data from the Phase 1b cohort will include but will not be limited to:

C_{max}	Maximum drug concentration in plasma on Cycle 1 Day 1 and Cycle 1 Day 8
t_{max}	Time to reach maximum (peak) drug concentration in plasma following drug administration on Cycle 1 Day 1 and Cycle 1 Day 8
$AUC_{(0-t)}$	Area under the concentration-time curve from zero time to time of last quantifiable concentration in plasma on Cycle 1 Day 1 and Cycle 1 Day 8
CCI	[REDACTED]

Other PK parameters may be calculated as appropriate.

Phase 2

Plasma concentrations of E7386 will be tabulated and summarized by dose level, day and time. Plasma concentrations will be summarized using descriptive statistics (number of subjects [n], mean, SD, minimum, median, maximum).

Plasma concentration data for E7386 in the Phase 2 part will be used to conduct population PK analysis and/or graphical presentation by integrating plasma concentration data from the Phase 1b part and/or other studies. PK/PD relationships (ie, exposure-efficacy, exposure-safety, and exposure-biomarker relationships) will be modeled, if possible, using a mechanistic approach, for effects of study treatment. Exploratory/graphical analyses will be conducted for PK/PD evaluations, and, if possible, will be followed by model-based analyses for E7386. For population PK, PK/PD, and exposure-response analysis, the details will be described in a separately prepared analysis plan and its report, and the results will not be included in the CSR.

5.5.2 Pharmacodynamic, Pharmacogenomic, and Other Biomarker Analyses

PD, pharmacogenomics, and other biomarker analyses may be performed and reported separately. Details of these analyses will be described in a separate analysis plan.

5.6 Safety Analyses

DLTs will be evaluated by the dose level (if applicable) and total for Phase 1b part on the DLT Analysis Set.

The Safety Analysis Set will be used for all other safety analyses. Safety variables will be summarized on an “as treated” basis within each cohort/tumor type, and for phase/overall (as needed) using descriptive statistics (n, mean, standard deviation, median, Q1, Q3, minimum, and maximum for continuous variables; numbers and percentages for categorical variables).

Safety variables include TEAEs, clinical laboratory results, vital signs, CCI [REDACTED]

[REDACTED] ECOG PS. If needed, the changes from baseline will also be summarized. The summary will be presented by each cohort/tumor type, and by phase/overall as appropriate.

Study Day 1 for all safety analyses will be defined as the date of the first dose of study drug.

5.6.1 Extent of Exposure

The duration of treatment, total number of doses/infusions, total doses, dose intensity, and relative dose intensity will be summarized. These variables are defined per subject as follow:

- Duration of overall treatment (days) = Date of last dose of any study drug – Date of first dose of any study drug + 1
- Duration of E7386 (days) = Date of last dose of E7386 – Date of first dose of E7386 + 1
- Duration of pembrolizumab (days) = Date of last administration of pembrolizumab – Date of first administration of pembrolizumab + 1
- Duration of both drugs (days) = Date of one of the study drug is first discontinued – Date of first dose of both study drugs + 1
- Number of administrations of pembrolizumab = Total number of IV administrations
- Total doses (mg) of E7386 (mg) = Sum of all the actual doses of E7386
- Dose intensity (mg/day) of E7386 = Total doses / Duration of E7386
- Relative dose intensity (%) of E7386 = $100 \times$ Dose intensity of E7386/ Planned starting dose for each cohort

The number (percentage) of subjects with dose interruption, dose reduction and treatment discontinuation due to adverse events (AEs) will be provided. To determine dose reductions and dose interruptions, the incorrect doses that were taken by mistake will not be taken into consideration. Dose reduction is only applicable to E7386, but not for pembrolizumab, as pembrolizumab dose is always 200 mg when it is administered.

Treatment interruptions are identified as zero doses which are preceded and followed by the same dose level.

- If the dose after the zero dose is lower than that before the zero dose, this dose change will be counted as a dose reduction, instead of a dose interruption.
- If the subject discontinued due to AEs from treatment permanently after the zero dose, it will be counted as a treatment discontinuation due to AEs, instead of a dose interruption.

For pembrolizumab, as long as a dose was administered for a cycle, then there is not an interruption for this cycle.

Subject data listings will be provided for all dosing records.

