5 STATISTICAL METHODS

Statistical analyses will be performed by the sponsor or designee after the data cutoff and the database is locked and released. An earlier database lock may also be performed for the purpose of writing a clinical study report (CSR). Statistical analyses will be performed using SAS software or other validated statistical software, as required.

Data cutoff for the primary analyses in the Phase 2 part for each tumor cohort will be performed based on the Efficacy Analysis Set when all subjects have a tumor assessment

until **CCI** and/or have adequate follow-up to be evaluated for DOR, or they have discontinued early due to any cause. The full final analysis will be performed after all subjects complete from the study.

All descriptive statistics for continuous variables will be reported using mean, standard deviation, median, first quantile (Q1), third quantile (Q3), minimum and maximum. Categorical variables will be summarized as number (percentage) of subjects.

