5.1.3 Exploratory Endpoints

5.2 Study Subjects

5.2.1 Definitions of Analysis Sets

5.2.2 Subject Disposition

The number (percentage) of subjects who were screened for the study (ie, those who signed informed consent), continued in the study after screening, failed screening, and the primary reason for screen failures will be presented.

The number (percentage) of subjects who were treated, continued, or discontinued study drug at data cutoff date, along with the primary reason for discontinuation from the study drug will be presented. The number (percentage) of subjects who discontinued treatment but were on survival follow-up at data cutoff date will also be provided.

The number (percentage) of subjects who were on study or off study (ie, discontinued from the study) at data cutoff date and the primary reason for discontinuation from study will be presented.

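### Does the dose-interruption rule in SAP 5.6.1 need a further category for holds that are never followed by another dose?

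*SAP*

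**What the plan says.** Section 5.6.1 (Extent of Exposure) sets out the output: "The number (percentage) of subjects with dose interruption, dose reduction and treatment discontinuation due to adverse events (AEs) will be provided". It then defines an interruption: "Treatment interruptions are identified as zero doses which are preceded and followed by the same dose level".

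Two bullets follow.
- If dosing resumes at a lower level than before the zero dose, "this dose change will be counted as a dose reduction, instead of a dose interruption".
- If the subject stops permanently because of adverse events after the zero dose, "it will be counted as a treatment discontinuation due to AEs, instead of a dose interruption".

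A separate sentence covers the infused drug: "For pembrolizumab, as long as a dose was administered for a cycle, then there is not an interruption for this cycle". The section closes with: "Subject data listings will be provided for all dosing records".

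Other sections bear on the same subjects.
- Section 5.2.2 (Subject Disposition) presents "The number (percentage) of subjects who were treated, continued, or discontinued study drug at data cutoff date", together with the main reason for stopping.
- Section 5.6.2.2 tabulates treatment-emergent events that led to an interruption, in the overview and by system organ class and preferred term.
- Section 5.3.3 says that no statistical comparison is planned.
- Sections 9 and 11 place derivation rules and table shells in separate documents.

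**The concern.** The definition has two sides: the same dose level must come before and after the zero dose. A hold with no later dose fails the second condition. The bullets re-file only one kind of hold with no later dose, the one that ends in a stop for adverse events. Two ordinary outcomes remain: a hold followed by a permanent stop for another reason, such as progression or withdrawal of consent, and a hold still open when the data are cut.

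The wording also invites a second reading. Both bullets say that the hold is counted elsewhere in place of an interruption, as if every hold were an interruption unless re-filed. On that reading the two remaining outcomes would count, and two programmers could report different numbers. Open holds could reach a published table, because Section 5 says: "An earlier database lock may also be performed for the purpose of writing a clinical study report (CSR").

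A smaller doubt concerns the sentence that announces the output: the reference to adverse events may limit all three items or only discontinuation.

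At stake is one exposure percentage. If such holds ought to count, the literal rule can only lower it.

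**Working it through.** The SAP states no figure for this output, so there is nothing to reproduce. The check is to apply the Section 5.6.1 rules literally to each way a hold of E7386 can end. Resumption at a higher level is left aside, because the SAP does not mention it.

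| How the hold ends | Same dose level afterwards? | Class under 5.6.1 | Where else the subject can be seen |
|---|---|---|---|
| Same level resumed | Yes | Interruption | Dosing listing |
| Lower level resumed | No | Reduction | Dosing listing |
| Permanent stop, adverse event | No later dose | Discontinuation due to adverse events | Disposition, with reason; dosing listing |
| Permanent stop, other reason | No later dose | Not an interruption; no bullet | Disposition, with reason; dosing listing |
| Open at data cutoff | No later dose yet | Not an interruption; no bullet | Disposition, as continuing; dosing listing |

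In every row, a hold caused by an adverse event can also appear in the Section 5.6.2.2 tables, which state no condition that dosing resumes.

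The last two rows are therefore settled: the hold is not an interruption. The three items in the output are interruption, reduction and discontinuation due to adverse events. The bullets can be read as sending holds that fail the definition to the other two items where they belong there. A stop for another reason belongs to neither, so it needs no bullet in this table.

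**Scale.** The count is per subject, so only a subject with no other qualifying hold is affected. With k such subjects among N, the percentage differs between the two readings by 100 × k / N points. Planned cohort sizes are blacked out in Section 4. N = 15 is the number of subjects per tumor cohort at the futility review (Section 6). N = 30, N = 40 and every k are assumptions.

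| k | N = 15 | N = 30 | N = 40 |
|---|---|---|---|
| 0 | 0 | 0 | 0 |
| 1 | 6.7 | 3.3 | 2.5 |
| 2 | 13.3 | 6.7 | 5.0 |

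As an invented example, take 30 subjects, 6 with a hold resumed at the same level and 2 others with only a hold that has no later dose. The literal reading gives 6/30 = 20.0% and the broader reading (6 + 2)/30 = 26.7%. The gap of 6.7 points comes entirely from choosing k = 2.

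**Effect of counting such holds.** If a hold before a non-adverse-event stop were made an interruption while the second bullet stayed, two identical final holds would be classed differently according to the reason for the later stop. If open holds were counted at cutoff, some would move later to reduction or discontinuation, so the figure could change between database locks. The present rule waits for the outcome. Open holds should mostly resolve by the full final analysis, which Section 5 places after all subjects have completed the study.

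**The case for a change.** The strongest argument for a change is internal to the text. Under the literal definition the second bullet is unnecessary, because a hold with no later dose already fails the test. Its presence suggests that the authors regarded holds as interruptions by default, so the two remaining outcomes were overlooked rather than excluded. In addition, a hold for an adverse event followed by a stop for another reason could appear in the Section 5.6.2.2 tables but not in the exposure count, so two tables in one report could disagree. If the last dose means the last non-zero dose, a final hold also leaves treatment duration and dose intensity unchanged, and those summaries would not show it either.

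Part of this stands. The text names no category for the two outcomes, the wording of the bullets leaves some room for doubt, and the scope of the adverse event qualifier is unclear. The conclusion that the count is understated does not follow. It assumes that a hold never followed by another dose ought to be an interruption, and no section says so. The second bullet itself declines to count such a hold when an adverse event ends treatment. A duration that stops at the last non-zero dose would point the same way, since final zero-dose days would fall outside treatment. A difference between an exposure table built from dosing records and an event table built from the action taken reflects two definitions and need not be an error.

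**Conclusion.** No change to the plan is needed. This is a fine point of derivation that the written definition already decides, and counting the extra holds would be a debatable choice rather than a correction. Following Section 5.6.1 as written gives a usable descriptive summary: an interruption is a pause after which the same dose level was resumed. Subjects whose last hold was not followed by a dose remain visible in the disposition table and the dosing listings. No comparison and no decision rule in the SAP uses the percentage.

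The size of any effect cannot be derived from the SAP. At N = 15 it is 6.7 points for each affected subject, and it is zero if no subject has only such a hold. This view assumes that the literal definition is the one programmed. The derivation documents named in Section 9 are not at hand and may say so outright. They and the table shells are the natural place to confirm that final holds are excluded and to label whether interruptions and reductions are for any cause or for adverse events only. The pembrolizumab sentence works per cycle and is less explicit about a missed last cycle, but the same reasoning applies.

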5.6.2 Adverse Events

5.6.2.1 Dose Limiting Toxicity

The number (percentage) of subjects with DLTs and reasons for DLTs will be summarized for DLT Analysis Set. Subject data listing will be provided for DLT records.

5.6.2.2 Adverse Events

The AE verbatim descriptions (investigator terms from the CRF) will be classified into standardized medical terminology using the Medical Dictionary for Regulatory Activities (MedDRA). AEs will be coded to the MedDRA lower level term (LLT) closest to the verbatim term. The linked MedDRA PT and primary system organ class (SOC) will also be captured in the database. The Common Terminology Criteria for Adverse Events ([CTCAE](#)) version 5.0 will be used to assess the severity of AEs.

A TEAE is defined as an AE that emerges during treatment (on or after the first dose date of study drug up to 30 days after the subject's last dose), having been absent at pretreatment (Baseline) or:

- Reemerges during treatment or up to 30 days following last dose of study drug, having been present at pretreatment (Baseline) but stopped before treatment, or
- Worsens in severity during treatment or up to 30 days following last dose of study drug relative to the pretreatment state, when the AE is continuous

The SAE is also counted as a TEAE if it emerges up to 90 days after the subject's last dose of study drug, or up to 30 days following cessation of study drug if the subject initiated new anticancer therapy, whichever is earlier.

Only those AEs that are treatment-emergent will be included in summary tables. All AEs, treatment emergent or otherwise, will be presented in subject data listings.

The incidence of TEAEs will be reported as the number (percentage) of subjects with TEAEs by SOC and PT. A subject will be counted only once within an SOC and PT, even if the subject experienced more than 1 TEAE within a specific SOC and PT. The number (percentage) of subjects with TEAEs will also be summarized by highest CTCAE grade.

An overview table, including the number (percentage) of subjects with TEAEs, TEAEs with CTCAE Grade 3 or above, treatment-emergent serious adverse events (SAEs), deaths, TEAEs leading to discontinuation from study drug, TEAEs leading to dose reduction, TEAEs leading to dose interruption, and TEAEs leading to dose reduction or interruption will be provided. Additionally, the TEAE by SOC and PT (any grade and grade ≥ 3 , maximum grade 3, 4 and 5), TEAE by decreasing frequency of PT (any grade and grade ≥ 3 , maximum grade 3, 4 and 5) will be summarized.

The number (percentage) of subjects with TEAEs leading to death, treatment-emergent serious adverse events (SAEs, fatal and non-fatal), TEAEs leading to discontinuation from study drug, TEAEs leading to dose reduction, TEAEs leading to dose interruption, and TEAEs leading to dose reduction or interruption will be summarized by MedDRA SOC and PT.

Similar summaries for treatment-related TEAEs will also be provided if deemed necessary. Treatment-related TEAEs include those events considered by the investigator to be related to study treatment (any study drug).

Subject data listings of all AEs, all AEs leading to death, all SAEs, and all AEs with CTCAE Grade 3 or above will be provided.

Subject data listings of AEs leading to discontinuation from study drug, AEs leading to dose reduction, AEs leading to drug interruption, and all deaths will be provided for all treated subjects.

TREATMENT-EMERGENT ADVERSE EVENTS OF CLINICAL INTEREST

TEAEs of special interest for E7386 will be identified based on the review of safety data by Clinical and Pharmacovigilance. **CCI**

TEAEs of special interest (AEOSI) for pembrolizumab will be summarized by the grouped terms and PT.

TREATMENT-EMERGENT ADVERSE EVENTS ASSOCIATED WITH COVID-19

COVID-19 related TEAEs will be summarized by PT and worst CTCAE grade. A subject data listing of COVID-19 related TEAE will be provided.

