3.1.2 Secondary Objectives

Phase 1b part only:

- To assess tumor response according to RECIST 1.1

Phase 1b and Phase 2 parts:

- To assess duration of response (DOR) according to RECIST 1.1 per tumor cohort
- To assess the disease control rate (DCR: the proportion of subjects with complete response [CR], partial response [PR], or stable disease [SD] after ≥ 5 weeks from the first dose) according to RECIST 1.1 per tumor cohort
- To assess the clinical benefit rate (CBR: the proportion of subjects with CR, PR, or durable SD [duration of SD ≥ 23 weeks]) according to RECIST 1.1 per tumor cohort
- To assess the safety and tolerability of E7386 in combination with pembrolizumab
- To evaluate the pharmacokinetic (PK) profile of E7386 when co-administered with pembrolizumab

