8 DEFINITIONS AND CONVENTIONS FOR DATA HANDLING

8.1 General Data Handling

Baseline

The baseline value is defined as the last non-missing value reported before first dosing.

Change from Baseline, Percent Change from Baseline

Change from Baseline is defined as post-baseline value minus baseline value.

Percent change from Baseline is defined as follows:

$$\% \text{ Change from baseline} = (\text{Change from baseline}/\text{Baseline}) * 100\%$$

The following factors will convert days to months or years:

$$1 \text{ month} = 30.4375 \text{ days}$$

$$1 \text{ year} = 365.25 \text{ days.}$$

Time (years) from first diagnosis to first dose is:

$$(\text{Date of first dose} - \text{Date of first diagnosis})/365.25.$$

Handling of Missing Data

No imputation will be performed for missing data.

Handling of Missing Dates

The following imputation algorithm will be used for partial or missing dates:

Date of Death (only for subjects that died)

- If only the day of the month is missing, the first of the month will be used to replace the missing day
- If both the day and the month are missing, "January 01" will be used to replace the missing information*
- If a date is completely missing, death date will be imputed as the last known alive date + 1 day

* The imputed death date will be compared with the last known alive date (date of censoring for survival). The maximum date (of the imputed death date, date of censoring for survival + 1) will be considered as the date of death.

Start Date of Subsequent Anticancer Therapy

- If only the day of the month is missing, the subsequent therapy will be assumed to start on the first of the month if this day is later than the last dosing date of study treatment. Otherwise, the subsequent therapy will be assumed to start on the next day of the last dosing date of study treatment

- If both the day and the month are missing, the subsequent therapy will be assumed to start on the "January 01" of the given year if this day is latter than the last dosing date of study treatment. Otherwise, the subsequent therapy will be assumed to start on the next day of the last dosing date of study treatment
- If a date is completely missing, it will be considered as missing

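### The 90-day SAE window drops to 30 days for any subject who starts new anticancer therapy, so SAEs on days 31-90 that precede that therapy leave the treatment-emergent tables

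*SAP*

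**What the plan says.** All references are to the SAP.

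- **General rule (Section 5.6.2.2).** An AE is treatment-emergent if it arises "on or after the first dose date of study drug up to 30 days after the subject's last dose".
- **Extension for serious events (same section).** "The SAE is also counted as a TEAE if it emerges up to 90 days after the subject's last dose of study drug", and the sentence continues: "or up to 30 days following cessation of study drug if the subject initiated new anticancer therapy, whichever is earlier".
- **What is tabulated.** "Only those AEs that are treatment-emergent will be included in summary tables".
- **What is listed.** "All AEs, treatment emergent or otherwise, will be presented in subject data listings". The section also provides a separate listing of all SAEs.
- **Therapy dates (Section 8.1).** Under "Start Date of Subsequent Anticancer Therapy", partial dates are imputed and a completely missing date stays missing.

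Safety and tolerability is the Phase 1b primary objective (Section 3.1.1) and a secondary objective in both parts (Section 3.1.2: "To assess the safety and tolerability of E7386 in combination with pembrolizumab").

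**The concern.** A longer window for serious events serves to capture toxicity that appears after dosing stops. Ending it when another anticancer treatment begins makes sense, because later events may be due to that treatment. The written rule does something different. Its shortened limit is counted from the end of study drug, and it applies to any subject who initiated new therapy, whether that therapy began before or after the SAE.

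An event is therefore classified by what happens to the subject afterwards. Therapy given on day 60 cannot have caused an SAE on day 45, yet it removes that SAE from the treatment-emergent SAE table and, if the event is severe enough, from the Grade 3 or above tables. The error can only lower the counts, and only in subjects who go on to further therapy.

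The classification can also change between analyses. Section 5 allows an earlier database lock for a clinical study report and a full final analysis later. With a data cutoff between day 45 and day 59, the day-45 SAE in this example would be treatment-emergent in the first report and not in the final one.

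**Working it through.** The SAP gives no figure of its own to reproduce on this point. The check applies the rule as written and compares it with a rule tied to the therapy start.

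**Inputs (Section 5.6.2.2).** The limit is 90 days without new therapy and 30 days with it, and the earlier of the two applies. Let *s* be the SAE onset day and *t* the therapy start day, both counted from the last dose. The last dose and the cessation of study drug are taken to be the same day.

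**Rule as written.**
- No new therapy: counted if *s* ≤ 90.
- New therapy initiated: counted if *s* ≤ min(90, 30) = 30. The start day *t* does not enter, and the earlier-of clause has no effect, because 30 is always the smaller number.

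**Rule tied to therapy start.** Counted if *s* ≤ min(90, max(30, *t* − 1)), or if *s* ≤ 90 with no new therapy.

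| SAE day *s* | Therapy day *t* | As written | Tied to therapy start |
|---|---|---|---|
| 20 | 40 | counted | counted |
| 45 | none | counted | counted |
| 45 | 60 | not counted | counted |
| 75 | 85 | not counted | counted |
| 45 | 20 | not counted | not counted |
| 95 | none | not counted | not counted |

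The rules differ only for SAEs after day 30, up to day 90, that precede the therapy. An SAE that follows the therapy after day 30 is excluded under both. An SAE up to day 30 is kept under both.

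**Days lost.** Days 31 to 90 make up 60 days. For therapy starting on day *t* within that span, the pre-therapy days lost are *t* − 31:
- *t* = 45: days 31-44, 14/60 = 23%
- *t* = 60: days 31-59, 29/60 = 48%
- *t* = 75: days 31-74, 44/60 = 73%
- *t* ≤ 31: none

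These are shares of calendar days. Turning them into SAE counts would need SAE rates, onset times and therapy start times, and the SAP gives none of these.

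**Other sections.** No other part of the SAP adds a timing condition to the SAE rule. By contrast, Table 2 in Section 5.4.3 handles new therapy by date: PFS is censored at the last adequate assessment up to the day the therapy starts. Section 8.1 already supplies a derived start date.

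**The case against.** The strongest reply is that the sentence may carry over the SAE collection window of the protocol, which is not at hand. If SAEs are collected only to day 30 in subjects who start new therapy, a change to the SAP alone recovers nothing. This stands as a limit on the remedy. It does not make the written rule sound, because that rule still depends on a later event.

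It can also be said that the consequences are modest. Affected events that were collected remain in the AE and SAE listings, safety is summarised descriptively, no statistical comparison is planned (Section 5.3.3), and DLTs are analysed on their own analysis set. All of this is correct. Still, incidence is read from the tables, and those are what lose the events.

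A reader might infer more than the text supports:

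- **That all SAEs before new therapy are lost.** Those up to day 30 are kept by the general definition.
- **That 23% to 73% of late SAEs disappear.** These are shares of days. They become shares of SAEs only if onset is uniform over days 31-90, which the SAP does not support.
- **That therapy begun long after day 90 removes every SAE from days 31-90.** The literal wording allows this, but it lets therapy shorten a window that has already closed. That is the least natural reading of a loosely worded sentence, so no weight is placed on it.
- **That fatal-event tables are seriously understated.** A subject who dies without starting new therapy keeps the 90-day window. Only an SAE that begins before the therapy and proves fatal after it is affected.
- **That sites will certainly have recorded the excluded events.** The SAP does not state the collection window.

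**Conclusion.** The point holds within limits. As written, an SAE on days 31-90 after the last dose that precedes new anticancer therapy is left out of the treatment-emergent tables because of that later therapy. The same SAE is counted in a subject who receives no further therapy. This is a defect in a stated rule, and it can only reduce the counts. That the earlier-of clause does no work suggests a cutoff at the therapy start may have been meant, but the SAP does not say so.

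The exposed period is 14, 29 or 44 of 60 days for therapy on day 45, 60 or 75. The number of SAEs involved is unknown. The conclusion rests on the literal wording, on taking last dose and cessation of study drug as the same day, and on the absence of a timing condition elsewhere in the SAP. The treatment-emergent SAE and Grade 3 or above summaries are affected; the ORR analysis is not. The rule should be corrected before the TEAE flag is programmed.

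**What to change.** Define the extended window by the actual start of new therapy. Suggested wording for Section 5.6.2.2:

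> An SAE is also a TEAE when its onset falls within 30 days after the last dose, or on days 31 to 90 after the last dose and before the start date of any new anticancer therapy.

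Three additions are needed:

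1. **Completely missing start date.** Section 8.1 leaves it missing, so the rule must say how these subjects are classified.
2. **Partial start dates.** Section 8.1 imputes them early (first of the month, 1 January, or the day after the last dose). Some SAEs that truly preceded the therapy may still be excluded, and the SAP should acknowledge this.
3. **Protocol alignment.** Check the wording against the protocol's SAE collection window, and reconcile the two if they differ.

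The cost in the SAP is one reworded sentence, a fallback for missing dates and a change to the TEAE flag derivation. SAE counts may become slightly less favourable. Only SAEs actually collected under the protocol can be recovered.
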